7.4 LONG-TERM FOLLOW-UP

For subjects who have not progressed and have not initiated subsequent cancer therapy, clinical, serum and radiological disease assessments will continue to be captured every 16 weeks \pm 2 weeks. Additional contact may be made as requested by the sponsor or the investigator to obtain disease and survival updates on an as-needed basis until the subject discontinues from the study.

The following data will be collected:

- SAEs assessed by the investigator as related to SRA737
- First subsequent cancer therapy (if applicable)
- Laboratory tests (blood samples):
 - Serum tumor markers (if applicable), unless PD was previously documented
 - CTCs (for mCRPC subjects only), unless PD was previously documented
- Clinical disease evaluations, unless PD was previously documented
- Radiographic disease assessments, unless PD was previously documented
- Disease and survival updates, where available

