--	--

Overview of assessments (cont'd):	Subjects without progressive disease (PD) at the time of SRA737 discontinuation will continue in Long-term Follow-up to undergo disease evaluations every 16 weeks (\pm 2 weeks) and have the following collected: radiological and clinical disease assessments, SAEs assessed as related to SRA737 by the investigator, first subsequent anticancer therapy, and blood for serum tumor markers (if applicable) and CTCs (for mCRPC subjects only) until disease progression or initiation of subsequent cancer therapy. Additional contact may be made as requested by the Sponsor or the investigator to obtain disease and survival updates on an as needed basis until the subject discontinues from the study.
Criteria for evaluation:	
Dose-Escalation variables:	All subjects receiving at least 75% of planned doses of SRA737 within Cycle 1 and those subjects receiving less than these planned doses of SRA737 due to dose-limiting toxicities (DLTs) will be evaluable for dose review decisions.
Efficacy variables:	All subjects who have measurable disease, receive at least 75% of 1 cycle of study medication and have a baseline assessment of disease plus at least 1 post-baseline assessment of disease will be evaluable for response. All subjects enrolled into one of the 6 indication-specific expansion cohorts will be evaluable for response if they have measurable, prospectively-selected genetically-defined tumors as specified in Section 4, received at least 75% of 1 cycle of study medication, have a baseline assessment of disease and at least 1 post-baseline disease assessment. In addition, subjects who have measurable disease and received at least 75% of 1 cycle of study medication but develop PD, intolerable toxicity, or death prior to the post-baseline assessment will also be considered evaluable and will be classified as nonresponders.
Safety variables:	All subjects who receive at least one dose of SRA737 will be evaluable for safety.

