3 TRIAL DESIGN

3.1 CLINICAL TRIAL OBJECTIVES AND ENDPOINTS

3.1.1 PRIMARY OBJECTIVES AND ENDPOINTS

Primary objectives	Endpoints
To establish the safety profile of SRA737	Safety parameters (referencing National Cancer Institute – Common Terminology Criteria for Adverse Events [NCI-CTCAE] v4.03) including: incidence, seriousness, severity and causality of each AE to SRA737, timing of AE onset, AE duration, and AEs leading to interruption, modification, or discontinuation of study treatment, and primary reason for discontinuation of study treatment if other than disease progression (PD), laboratory (eg, clinical chemistry, hematology, urinalysis) and vital sign data
To determine the MTD with 1 or more schedules of administration of SRA737	The highest dose at which $\leq 33\%$ of subjects have a dose limiting toxicity (DLT) in a cohort of up to 6 subjects
To propose a recommended Phase 2 dose and schedule of SRA737	A safe and well tolerated dose and schedule that provides high exposure, based on all available PK, PDn, and safety parameter data from all cycles of therapy
To evaluate the preliminary efficacy of SRA737 including efficacy in prospectively-selected genetically-defined subjects enrolled into indication-specific expansion cohorts	Objective response rate (ORR) Disease control rate (DCR) Time to response (TTR) Duration of response (DOR) Progression-free survival (PFS) Time to progression (TTP) Overall survival (OS)

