5.7 DISCONTINUATION FROM THE STUDY

Subjects will be followed according to the procedures described in Section 7.4 until disease progression, initiation of subsequent cancer therapy, or the subject is discontinued from the study for any of the reasons described below.

Subjects have the right to withdraw from the study at any time and for any reason without prejudice to their future medical care by the physician or at the institution. All study-related assessments and data collection will cease.

The investigator must make every reasonable effort to complete study-specified Safety Follow-Up assessments at 30 days \pm 7 days after last SRA737 administration. However, if the investigator removes a subject from the study or if the subject declines further participation prior to the planned Safety Follow-Up visit, the Safety Follow-Up assessments

should be performed before withdrawal from the study whenever possible. All results of the evaluations and observations, together with a description of the reasons for withdrawal from the study, must be recorded in the medical records and in the eCRF.

Subjects may be discontinued from the study for the following reasons:

- Withdrawal of consent
- Death or loss to follow-up
- Sponsor's decision to terminate the study

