### 11.4. Overall Survival (OS)

Overall survival is defined as time from the Cycle 1 Day 1 to the date of death. If a subject doesn't have a recorded death in the database, OS will be censored at the date at which the subject is last known to be alive. The last known alive date is based on searching the last date from the following CRF forms:

- Treatment start and end date from the continuous dosing page
- Treatment start date from the first dose page
- Date of off-treatment

- Date of follow-up or date of death from the follow-up page
- Date of visits

OS will be analyzed using the Kaplan-Meier method. The output will include count and percentage of subjects with death or censored outcome. Median OS and 95% CI based on log-log transformation will be provided. Landmark analyses at various timepoints may be carried out if of clinical interest. Kaplan-Meier plot supporting the table summary may also be generated.

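### OS is a primary-objective endpoint, but survival contact after progression or new therapy is optional, so Kaplan-Meier censoring is informative: probably biased upward, downward if deaths are reported more readily than alive status

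*Protocol*

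**What the plan says.** Protocol 3.1.1 lists OS among the seven endpoints of the preliminary-efficacy objective, one of the primary objectives. SAP 4.1 lists it under primary endpoints, and SAP 16 gives it its own table, listing and Kaplan-Meier figure.

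Scheduled follow-up is narrower than that endpoint needs:

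- Protocol 7.4 applies the 16-weekly assessments to a restricted group: "For subjects who have not progressed and have not initiated subsequent cancer therapy". The synopsis agrees: "Subjects without progressive disease (PD) at the time of SRA737 discontinuation will continue in Long-term Follow-up".
- Protocol 5.7 sets the end of that follow-up: "until disease progression, initiation of subsequent cancer therapy, or the subject is discontinued from the study for any of the reasons described below".
- Beyond it, Protocol 7.4 permits extra contact "to obtain disease and survival updates on an as-needed basis until the subject discontinues from the study", and the data item is "Disease and survival updates, where available". The matching row of the schedule in 7.6 carries the same qualifier.
- Protocol 7.3 requires a Safety Follow-up visit 30 ± 7 days after last dose, whatever the reason for stopping. Protocol 10.2.2 collects adverse events to 30 days after last dose.

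For the analysis, SAP 11.4 states that "OS will be censored at the date at which the subject is last known to be alive". It searches dosing, off-treatment, follow-up and visit dates, and reports a median with a 95% CI. Protocol 11.2.3 censors at the last visit at which survival status was established. Neither document gives an interval for survival contact after progression, a status check at data cut-off, or a sensitivity analysis for this censoring.

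**The concern.** Kaplan-Meier assumes that subjects censored at a given time have the same future risk as those still observed. Here the event that ends required contact is progression or a new therapy, and both mark a worse or at least different prognosis. Treatment normally runs to progression (Protocol 5.3), so a typical progressor stops dosing, attends the safety visit about a month later, and then has no required contact. The late risk set is therefore weighted towards subjects who have not progressed.

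At stake is whether the OS median, interval and curve of a primary-objective endpoint describe survival, or describe which subjects sites happened to hear about.

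**Working it through.** The documents state no expected OS median, event count or power, so there is no OS figure to reproduce. The check asks how far, and in which direction, Kaplan-Meier moves when post-progression status is incomplete.

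**Assumptions (not from the documents).** Exponential time to progression, median 60 d: λ = ln 2/60 = 0.01155. Exponential post-progression survival, median 140 d: μ = ln 2/140 = 0.00495. Progressors who are not contacted are censored 30 d after progression, to reflect the safety visit. Observation ends at 720 d.

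**True survival.** S(t) = (λe^(−μt) − μe^(−λt))/(λ − μ). S(233) = 0.501 and S(234) = 0.499, so the true median is just under 234 d.

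**A. No contact after the safety visit (extreme case).** For t > 30 the observed risk set holds progression-free subjects and those who progressed within the last 30 d. The ratio of the second group to the first is constant: λ(e^(30(λ−μ)) − 1)/(λ − μ) = 1.75 × 0.219 = 0.383. Only the second group can die, so the estimated hazard is 0.00495 × 0.383/1.383 = 0.00137 per day. The first 30 d contribute about 0.022 to the cumulative hazard. The median solves 0.022 + 0.00137(t − 30) = 0.693, which gives t ≈ 519 d with unrounded values. Simulation of 400,000 subjects gives 513 d; few subjects remain in that tail.

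**B. A random share of progressors followed.** The same hazard argument, with followed progressors kept in the risk set:

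| Share followed | Simulated median (d) | Formula (d) | True (d) |
|---|---|---|---|
| 0% | 513 | 519 | 234 |
| 25% | 290 | 291 | 234 |
| 50% | 259 | 260 | 234 |
| 75% | 243 | 244 | 234 |

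At 50% the excess is 259 − 234 = 25 d, or 11%. At 75% it is 9 d, or 4%.

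**C. Some deaths without prior progression.** If 10% of first events are such deaths, they are observed without extra contact. The no-contact hazard for t > 30 becomes (0.1λ + μ × 0.9 × 0.383)/(1 + 0.9 × 0.383) = 0.00213. The median reads about 332 d (331 and 334 d in two simulations) against a true 213 d. The extreme in A is therefore sensitive to this share.

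**D. Selective death reporting.** Suppose later deaths are reported with some probability, living subjects are never updated and stay censored 30 d after progression, and data cut-off falls 90–720 d after entry. With 25, 50, 75 or 100% of later deaths reported, the median reads about 265, 232, 215 or 204 d against 234 d. With cut-off at 90–450 d, it reads about 252, 218 and 189 d for 25, 50 and 100%. Reported deaths stay in the risk set until they occur while comparable living subjects leave it, so the bias turns downward.

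**E. Values nearer the protocol's ovarian benchmarks.** Protocol 2.2.2 gives PFS of 3–4 months and OS under 12 months for platinum-resistant disease. Taking PFS 3.5 and true OS 11.0 months, with 5–15% deaths without progression, the median reads 17.6–26.1 months with no later data, 12.1–12.5 with a random 50% followed and 11.3–11.5 with a random 80%. Under selective death reporting (10% deaths without progression, cut-off 3–15 months after entry), 25, 50, 75 or 100% of later deaths reported gives 11.9, 10.1, 9.2 or 8.6 months. The pattern is the same.

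**The case against.** **Later survival data are allowed.** Progression is not among the reasons for study discontinuation listed in Protocol 5.7. The survival-update row in 7.6 lacks the footnote that stops disease assessments at progression. SAP 11.4 draws on a follow-up form that records deaths, and SAP 16.3 lists deaths for all subjects. This stands: later data may exist and may be substantial. But nothing requires them, and Protocol 5.7 can be read as ending the 7.4 procedures at progression.

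**The direction is not fixed.** A reader might infer that OS will certainly read too long. The documents do not support that, because the direction depends on whether deaths or alive updates arrive more readily, and no procedure governs either. Upward is the likelier direction if contact simply lapses.

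**Censoring does not fall at progression itself.** A reader might infer that subjects drop out at the moment their risk rises. The safety visit and 30-day event collection carry most subjects about a month past stopping. Monthly follow-up of SAEs, and of drug-related AEs present at that visit, takes some further. The calculations above already include the 30 days.

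**The bias may be small beside sampling error.** With 20 subjects and even 20 deaths, an approximate exponential 95% interval for a median spans a factor of exp(1.96/√20) = 1.55 each way, against 11% at 50% random follow-up. This stands for a single cohort with reasonable ascertainment. It does not cover low or selective ascertainment, and bias does not shrink when tumor types are pooled in the overall column.

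**OS drives no decision.** Sizing rests on ORR precision, and SAP 9.1.2 calls p-values and intervals supportive. That limits the consequence, but a descriptive survival curve should still describe survival.

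**Conclusion.** The point holds as a gap in follow-up that makes OS censoring informative. Scheduled contact stops at progression or new therapy, the SAP censors at the last known alive date, and nothing in the plan measures or bounds the effect.

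The size depends on ascertainment rates that the documents do not give. In the illustration it runs from about 4% too long (75% of progressors followed at random) to more than double (no contact, no deaths before progression), and to about 13% too short ((234 − 204)/234, all later deaths but no alive updates, cut-off 90–720 d). All rest on exponential times and assumed medians. The no-contact figure is an extreme, not a forecast.

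A reader might go further and call OS uninterpretable. That does not follow across this range: with most progressors followed irrespective of outcome, the bias is modest. What cannot be known from the plan is which part of the range applies. This is a cheap improvement for a primary-objective endpoint, not a flaw that undermines the trial.

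**What to change.** **While subjects can still be contacted.** In Protocol 7.4 and the 7.6 schedule, record survival status by phone, clinic record or public record for every treated subject at the existing 16-week interval, regardless of progression or new therapy, until death, withdrawal of consent or study end. Align 5.7 with this. Do one survival sweep in a fixed window before each data cut-off. In SAP 11.4, censor at the last such survival contact.

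**If collection is already over.** SAP 9.2.1 quotes entries from the clinical database, so this may be the case. In SAP 11.4, report the share of subjects censored within a stated time of progression. Add two bounds: subjects censored after progression treated as dying soon after censoring, and the same subjects treated as surviving to cut-off. This keeps OS and shows the reader how much rests on missing follow-up, so OS need not be dropped from the endpoints.

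**Cost.** A short contact or record check per subject every 16 weeks, with no added visit or procedure. The second route costs one extra table and two reruns of the Kaplan-Meier program.

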7.5 MISSED EVALUATIONS

Missed evaluations should be rescheduled and performed as close to the originally scheduled date as possible. Based on the investigator's judgment, an exception can be made when rescheduling becomes medically unnecessary or unsafe because it is too close in time to the next scheduled evaluation. In that case, the missed evaluation may be omitted.

7.6 SCHEDULE OF EVENTS

Observation / Investigation	Screening evaluations – to be within [x] days of first dose (as noted)			First dose for Intensive PK	Treatment phase (28-day cycle) Evaluations for each day				Safety Follow-up	Long-term Follow-up
	N/A	28 days	7 days		Single day, Day -7 to Day -4	1	8	15		
Written informed consent	X									
Demographics		X								
Medical history		X								
Adverse event evaluation	SAEs from informed consent. AEs from first dose of SRA737. Continually review							X (b)	X(c)	
Concomitant treatments	From date of informed consent. Continually review								X(c)	
Availability / Submission of tumor tissue and ctDNA for tumor profiling (d), and MSI status (e)	X									
Determination of HPV status (HNSCC and SCCA)	X									
Radiological disease assessment		X (f)				End of every 8 weeks (± 1 week) from C1D1		X (f, m)	X (f, m)	
Clinical disease assessment (if applicable)			X			End of every 4 weeks (± 1 week) from C1D1		X (m)	X (m)	
Disease and survival updates (where available)									X	
Physical examination (g)			Complete			Symptom-directed, predose on D1 of each cycle - repeat as clinically indicated		Symptom-directed		
Temperature, seated BP, and pulse				X (a)	X	C1	C1	C1	X	
Height				X (a, n)						
Weight				X (a, n)					X	
WHO performance status			X	X (a)	X				X	
ECHO (h)		X			C2				X	

Observation / Investigation	Screening evaluations – to be within [x] days of first dose (as noted)			First dose for Intensive PK	Treatment phase (28-day cycle) Evaluations for each day				Safety Follow-up	Long-term Follow-up
	N/A	28 days	7 days		Single day, Day -7 to Day -4	1	8	15		
ECG (i)		X (Locally-read)			Refer to Section 7.7 for time points (local and central)					X (Locally-read)
Pregnancy test (j)			X	X (a, n)					X	
Serum tumor markers (if applicable, eg, CA-125, PSA, CEA, CA19-9, AFP, others as indicated)				X (a, n)	End of every 4 weeks (\pm 1 week) from C1D1					X (m)
Samples for biochemistry			X	X (a)	X (k)	X (k)	X (k)	X (k)	X	
Samples for hematology			X	X (a)	X (l)	X (l)	X (l)	X (l)	X	
Troponin T or I				X (a)	C1 C2 C6	C1			X	
Urine sample for urinalysis				X (a)	X				X	
Blood sample for CTCs (mCRPC subjects only)	X			X (a, n)	End of every 4 weeks (\pm 1 week)					X (m)
Blood sample for ctDNA for exploratory analysis	Refer to Section 7.7 for time points							X		
Blood sample for Exploratory Analyses (Mutational Burden)	Refer to Section 7.7 for time points							X		
Tumor Tissue for Optional Exploratory PD	Refer to Section 7.7 for time points									
Blood sample for PK				Refer to Section 7.7 for time points						
SRA737 administration				X (a)	Continuous daily dosing or as specified in alternate dosing schedule					
SRA737 Diary Card					Should be reviewed at each visit				X	

- a. Assessments scheduled to occur for the first dose for PK (given on a single day between Day -7 to Day -4) will be conducted on the first day of dosing unless performed within 72 hours prior or noted otherwise for the specific assessment in Section 7.2.1. Dosing should be delayed if eligibility criteria are no longer met. The Sponsor may eliminate or modify the requirements for the Day -7 to Day -4 visit once sufficient data to evaluate the single-dose PK of SRA737 have been analyzed.
- b. Monthly follow up is required for all SAEs and for those AEs considered drug related (highly probable, probable or possible) and present at the SFU visit. Monthly follow-up will continue until the event resolves, returns to baseline, stabilizes, or the subject discontinues from study.
- c. Only new SAEs assessed by the investigator as related to SRA737 and first subsequent anticancer therapy will be collected.
- d. Availability of suitable archival tumor tissue or planned biopsy for fresh tumor tissue acquisition for tumor profiling must be confirmed. When archival material was collected more than 18 months ago, the ability to collect fresh tumor tissue should be discussed with the sponsor. Submission prior to or during Screening (the 28-day window does not apply) with confirmation of positive results is required to determine eligibility for Expansion Cohort subjects. Archival tumor tissue should be requisitioned for submission by Cycle 1 Day 1 for Dose Escalation subjects. See Section 7.1.1 for more details. A blood sample for ctDNA tumor profiling will be obtained from all screened subjects within 28 days prior to the first dose. If prospective analysis is performed, results must be available prior to the first dose of SRA737. If retrospective analysis will be performed, results are not required to be available prior to the first dose of SRA737.
- e. For CRC subjects and other subjects as clinically relevant whose MSI status is unknown, determination of MSI status will be performed on archival tumor tissue or fresh tumor tissue submitted for tumor profiling during Screening.
- f. Screening assessment to be conducted within 35 days of Cycle 1 Day 1. Follow-up radiological assessments must be repeated at the end of every 8 weeks (\pm 1 week) after Cycle 1 Day 1. Subjects with bone metastases being followed by bone scans will have scans every 8 weeks (\pm 1 week) for the first 6 months and then every 16 weeks (\pm 2 weeks) thereafter. During Long-term Follow-up, assessments will be done every 16 weeks, unless requested more frequently by the sponsor or investigator. Assessment may be discontinued if PD was shown on a previous scan.
- g. Complete physical examination to be performed within 7 days of the first dose. Subsequent examinations on Day 1 of each cycle (and additionally as clinically indicated) may be symptom directed.
- h. ECHO will be done at Screening, Cycle 2 Day 1 (\pm 3 Days), and at the SFU visit. All subsequent cardiac monitoring will be done at the investigator's discretion.
- i. All subjects will have locally-read ECGs. Centrally-read ECGs will also be performed - see Section 7.7 for detailed time points. Centrally-read ECGs may be eliminated by the Sponsor once sufficient data have been collected and analyzed. If this occurs, the modified requirements will be documented by an update to the appropriate study documents.
- j. Pregnancy test: For women of childbearing potential. More frequent pregnancy tests may be conducted if required per local regulations.
- k. Biochemistry should be performed on Days 1, 8, 15 and 22, during Cycles 1 and 2. The frequency can be reduced to Days 1 and 15 from Cycle 3 onwards at the discretion of the investigator, and reduced again to once a month (predose on Day 1) from Cycle 7 onwards. Laboratory tests can be performed up to 72 hours prior to the first dose of each cycle (Day 1).
- l. Hematology should be performed on Days 1, 8, 15 and 22, during Cycles 1 to 3. Hematology assessments will be repeated weekly for the cycle following an intra-subject dose escalation, where applicable. The frequency can be reduced to Days 1 and 15 from Cycle 4 onwards at the discretion of the investigator. Laboratory tests can be performed up to 72 hours prior to the first dose of each cycle.
- m. Disease assessments will be discontinued in the case of PD or if subsequent anti-cancer therapy is initiated.
- n. Assessment to be carried out on Cycle 1 Day 1 in the event the Day -7 to Day -4 visit is eliminated.

